1. STUDY DESIGN

1.1. STUDY OBJECTIVES

1.1.1. Primary Objective

The primary objective of the study is to evaluate the efficacy in terms of the percentage of subjects achieving an ACR20 response, of different doses and dose regimens of GLPG0634 compared to placebo at Week 12.

1.1.2. Secondary Objectives

The secondary objectives of the study are:

- To evaluate the efficacy in terms of the percentage of subjects achieving an ACR20, ACR50, ACR70, ACR-N, DAS28(CRP), EULAR response and ACR/EULAR remission, CDAI, and SDAI with different doses and dose regimens of GLPG0634 compared with placebo at every visit.
- To evaluate the safety and tolerability of different doses of GLPG0634 in comparison with placebo.
- To characterize the population PK and PD of GLPG0634 and its metabolite (G254445) in subjects with rheumatoid arthritis and investigate the relationship between exposure and efficacy/safety/PD.
- To evaluate the effects of different doses and dose regimens of GLPG0634 administration on subjects' disability, fatigue, and quality of life.

1.2. STUDY DESIGN

This is a multicenter phase IIb, double-blind, placebo-controlled, monotherapy study in subjects with moderately to severely active RA who have an inadequate response to MTX alone. A total of 280 subjects will be randomized to one of 3 q.d. dose regimens of GLPG0634 (50 mg q.d., 100 mg q.d., 200 mg q.d.) or to placebo. Treatment duration will be 24 weeks. At Week 12, all subjects on placebo and the subjects on the 50 mg dose who have not achieved a 20% improvement in swollen joint count (SJC66) and tender joint count (TJC68) will be assigned (automatically via interactive voice/web response system [IXRS]) to 100 mg q.d. in a blinded fashion and will continue the study until Week 24. Subjects in the other groups will maintain their randomized treatment until Week 24.

[figure not shown]
At completion of the 24 week treatment period, subjects may be offered the option to enter a Long Term Follow-up study (GLPG0634-CL-205). This Long Term Follow-up study is subject to separate approval from Regulatory Agencies and Ethics Committees.

Data from the Long Term Follow-up study 205 will be presented in a separate analysis, and is not part of this SAP.

Subjects participating in the 204 study will be requested to attend a total of 11 visits throughout the study: Screening visit (up to 28 calendar days before Baseline visit), Baseline visit, Week 1 visit, Week 2 visit, Week 4 visit, Week 8 visit, Week 12 visit, Week 16 visit, Week 20 visit, Week 24 visit, and for the subjects not entering the Long Term Follow-up study (GLPG0634-CL-205), a Follow up visit 7 to 10 calendar days after end of study

treatment. Consequently, each subject will remain in the study for approximately 29 weeks (from Screening visit to Follow-up visit).

GLPG0634-CL-204 (DARWIN 2): monotherapy:

Notes:

- R = (re)randomization.
- Responder: at least 20% drop in TJC68 and SJC66 versus baseline.

1.3. PROTOCOL AND PROTOCOL AMENDMENTS

Protocol Versions	Date (ddMMMyyyy)
Final 1	14MAR2013
Amendment 1	11APR2013
Amendment 2	17APR2013
Amendment 3	02AUG2013
Amendment 4	20NOV2013
Amendment 5	23MAY2014

Note: further local amendments are not listed here.

This SAP was based on the latest version of the protocol (Amendment 5, 23MAY2014).

1.4. FLOWCHART

Event	Screening	Baseline ¹	Treatment period ²									FU visit ³
			D8/ W1	D15/ W2	D29/ W4	D57/ W8	D85/ W12	D113/ W16	D141/ W20	D169/ W24	EDV ⁴	
Informed consent	Written informed consent will be obtained before any study-related procedures and/or assessments are performed.											
Inclusion/exclusion criteria	X	X ⁵										
Demographic data and baseline disease characteristics	X											
Medical history/concomitant illnesses	X											
Physical examination	X ⁶	X					X			X	X	X
Serology ⁷	X											
TB test and chest X-ray ⁸	X											
Pregnancy test ⁹	X	X	X	X	X	X	X	X	X	X	X	X
12-Lead ECG	X						X			X	X	X
Vital signs ¹⁰	X	X	X	X	X	X	X	X	X	X	X	X
Clinical laboratory tests ¹¹	X	X	X	X	X	X	X	X	X	X	X	X
PK blood samples ¹²					X		X			X	X	
PD blood samples ¹³		X	X		X		X			X	X	

¹ Subjects will begin to take their treatment on the next morning (Day 1) following randomization.

² During the treatment period, a visit time window of ± 2 calendar days is allowed.

³ Follow-up visit will be performed only for subjects discontinuing prematurely from the study and for subjects not entering the Long Term Follow-up study GLPG0634-CL-205.

⁴ Early discontinuation visit.

⁵ Eligibility criteria check based on the laboratory results from the Screening visit.

⁶ At Screening, includes height and weight.

⁷ Includes Hepatitis B and C, HIV 1 and 2, RF, and anti-CCP.

⁸ X-ray should be performed if results from an X-ray performed in the previous 3 months are not available at the site.

⁹ For female subjects only. To be performed on serum at Screening and Week 24/EDV and on urine for other visits.

¹⁰ Vital signs are defined as blood pressure (systolic and diastolic), HR, and oral temperature.

¹¹ Refer to Section **Error! Reference source not found.**

¹² PK samples: 1 blood sample (2 mL) for analysis of GLPG0634 and its main metabolite (G254445) in plasma.

¹³ PD samples: 4 blood samples (2x4 mL for serum preparation and 2x2.5 mL in PAXgene tubes) will be collected for analysis of serum (analytes and miRNA profiling) and whole blood (gene expression in circulating leukocytes, mRNA and miRNA profiling).

Event	Screening	Baseline ¹⁴	Treatment period ¹⁵									FU visit ¹⁶
			D8/ W1	D15/ W2	D29/ W4	D57/ W8	D85/ W12	D113/ W16	D141/ W20	D169/ W24	EDV ¹⁷	
Randomization		X ¹⁸					X ¹⁹					
IXRS call	X	X	X	X	X	X	X	X	X	X	X	
Dispense study medication		X	X	X	X	X	X	X	X			
Subject diary card dispensation ²⁰		X	X	X	X	X	X	X	X			
Subject diary card collection			X	X	X	X	X	X	X	X	X	
Drug accountability check			X	X	X	X	X	X	X	X	X	
Study medication dosing												
Serum CRP	X	X	X	X	X	X	X	X	X	X	X	
SJC66	X	X	X	X	X	X	X	X	X	X	X	
TJC68	X	X	X	X	X	X	X	X	X	X	X	
Physician's Global Assessment		X	X	X	X	X	X	X	X	X	X	
Patient's Global Assessment	X	X	X	X	X	X	X	X	X	X	X	
HAQ-DI		X	X	X	X	X	X	X	X	X	X	
FACIT fatigue scale		X			X		X			X	X	
SF-36 questionnaire		X			X		X			X	X	
AE assessment												
Concomitant medications												

¹⁴ Subjects will begin to take their treatment on the next morning (Day 1) following randomization.

¹⁵ During the treatment period, a visit time window of ± 2 calendar days is allowed.

¹⁶ Follow-up visit will be performed only for subjects discontinuing prematurely from the study and for subjects not entering the Long Term Follow-up study GLPG0634-CL-205.

¹⁷ Early discontinuation visit.

¹⁸ Upon qualification for the study.

¹⁹ At Week 12, all subjects on placebo and the subjects on the 50 mg dose who have not achieved a 20% improvement in SJC66 and TJC68 will be assigned (automatically via IXRS) to 100 mg q.d. in a blinded fashion and will continue in the study until Week 24.

²⁰ Subject diary card will be dispensed to subjects on D -1 and at every following visit; subjects should be instructed to bring their diary card along with them to all visits.

2. ANALYSIS POPULATIONS AND TREATMENT GROUPS

2.1. ANALYSIS CHAPTERS

Each part of the analysis will consist of 2 or 3 main chapters:

1. Chapter 1: Period 1 of the study (up to and including Week 12): safety
2. Chapter 2: The study as a whole (periods 1 and 2 together, spanning the entire 24 weeks): safety & efficacy
3. Chapter 3: Period 2 of the study (from Week 12 until the end of the study): only for efficacy and adverse events.

Each analysis chapter will use its own set of “treatment groups” and imputation methods. Later in this document, when all parameters are analyzed separately, will be mentioned which is the primary.

2.1.1. Efficacy data

Study period	Treatment groups	Analysis populations	Imputation method
“Chapter 2”: Periods 1+2 together (full 24 weeks period)	
The 4 original groups:
 
 – Placebo¹ – GLPG0634 50 mg q.d. – GLPG0634 100 mg q.d. – GLPG0634 200 mg q.d. 
For the subjects in the placebo and low dose groups who switched to 100 mg/day during the second study period: they will be handled as if they discontinued at Week 12, and will be imputed from Week 12 onwards in the second study period. (Details: see further in the SAP)
	
ITT: all subjects randomized, exposed at least once, and with post-baseline data for at least one efficacy parameter.
 
Per-protocol: subpopulation of ITT, excluding all critical (=major) protocol deviations. This is decided during the blind review meeting before final database lock.
	
Observed case, non-responder imputation (NRI), last observation carried forward (LOCF): depending on the parameter; is specified later when all parameters are discussed.

¹ Note that all placebo subjects switch to 100 mg q.d. after Week 12. As a result, no “placebo” group will be presented after Week 12 in the tables and figures.

Study period	Treatment groups	Analysis populations	Imputation method

“Chapter 3”: Period 2, as of Week 12
	
The Week 12 responders, remaining on the same treatment during the second study period: 4 treatment arms:
 
 – Placebo switched to GLPG0634 100 mg q.d. – Continued GLPG0634 50 mg q.d. – Continued GLPG0634 100 mg q.d. – Continued GLPG0634 200 mg q.d. 
This analysis will show whether Week 12 responders remain responders when treatment is continued unchanged.
 
The Week 12 non-responders, either “switching” to 100 mg/day or continuing the same mid/high dose during the second study period: 4 treatment arms:
 
 – Placebo switched to GLPG0634 100 mg q.d. – GLPG0634 50 mg q.d. switched to GLPG0634 100 mg q.d. – Continued GLPG0634 100 mg q.d. – Continued GLPG0634 200 mg q.d. 
This analysis will show whether Week 12 non-responders start to respond when either treated for a longer period with the same mid/high dose, or have a dose increase to 100 mg/day.
	
ITT: all subjects randomized, exposed at least once, and with post-Week 12 data for at least one efficacy parameter. Subjects who discontinued prior the Week 12 visit will be excluded from this analysis.
	
Observed case, non-responder imputation (NRI), last observation carried forward (LOCF): depending on the parameter; is specified later when all parameters are discussed.

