Study Population (continued):	

• current or previous RA treatment with a biologic DMARD, with the exception of biologic DMARDs: administered in a single clinical study setting, and; more than 6 months prior to Screening (12 months for rituximab or other B cell depleting agents), and; where the biologic DMARD was effective, and if discontinued, this should not be due to lack of efficacy,

• previous treatment at any time with a cytotoxic agent, other than MTX, before Screening.

Primary Endpoint:	Percentage of subjects achieving an ACR20 response at Week 12
Secondary Endpoints:	Percentage of subjects achieving ACR20 response at Week 24, percentage of subjects achieving ACR50, ACR70, ACR-N, the DAS28(CRP), EULAR response and ACR/EULAR remission, CDAI, SDAI, the change from Baseline in Quality of Life (functional assessment of chronic illness therapy [FACIT] and Short Form-36 [SF-36]) scores at Weeks 1, 2, 4, 8 12, and 24, as appropriate.
Efficacy analysis:	The efficacy analysis will be performed on all subjects who used the study medication at least once and have post-Baseline efficacy data. Efficacy data (ACR20, ACR50, ACR70, ACR-N, EULAR response and ACR/EULAR remission, DAS28[CRP], components of the ACR, and DAS28, CDAI, and SDAI at each post-dosing visit) will be analyzed descriptively. Between-group comparisons will also be done for each dose group versus the placebo group. The effects of different doses of GLPG0634 administration on subject's disability, fatigue, and quality of life will also be evaluated. Hommel's closed-testing correction procedure will be applied to adjust for multiplicity. This study is not powered for any formal comparison among the GLPG0634 dose groups. Differences will be explored descriptively. No adjustment for multiplicity will be done for these exploratory differences.
Safety analysis:	Assessment of adverse events, laboratory parameters, vital signs, physical examination, and electrocardiograms. The safety analysis will be performed for all subjects who used the study medication at least once.

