#### **8.8.1.1 Datasets or Populations Analyzed**

All randomized subjects who received at least one dose of study medication and have at least one post-Baseline efficacy assessment will be included in the efficacy analysis (intent-to-treat [ITT]).

A secondary per-protocol analysis will be performed to confirm the ITT analysis, excluding subjects with major protocol deviations (such as Baseline CRP within normal range, Baseline TJC68 <8, Baseline SJC66 <6, <80% study medication compliance, or use of forbidden concomitant medications). Full details of the major protocol deviations will be described in the statistical analysis plan, with adherence to analysis sets agreed upon prior to database lock and unblinding.

All randomized subjects who received at least one dose of study medication will be included in the safety analysis.

All randomized subjects who received at least one dose of GLPG0634 and who have at least one PK measurement will be included in the PK analysis.

Reasons for study termination will be tabulated.

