## **Methods of Analysis**

Efficacy data (ACR20, ACR50, ACR70, ACR-N, DAS28[CRP]), EULAR response, and ACR/EULAR remission, and components of the ACR, CDAI and SDAI at each post-dosing visit) will be analyzed descriptively.

Between-group comparisons will be done for each dose group versus the placebo group. Hommel's closed-testing correction procedure (as implemented in SAS PROC MULTTEST) will be applied to adjust for multiplicity.

This study is not powered for any formal comparison among the GLPG0634 dose groups. However, differences between the dose groups will be calculated and presented with a 95% confidence interval. No adjustment for multiplicity will be done for these exploratory differences.

All subjects from the placebo group and nonresponding subjects from the 50 mg group who are reassigned to 100 mg at Week 12 will be handled as follows:

- Their Week 12 value will be carried forward in the original treatment group to all further time points (and between-group comparisons) after Week 12.
- Their actual assessments on Weeks 16, 20, and 24 will be analyzed descriptively as these represent their response after 12 weeks of GLPG0634 exposure after first having received placebo or failed on a low dose.

Analysis methods per post-Baseline time point:

- Binary parameters: logistic regression model with factors treatment, region and previous use of biologics.
- Continuous parameters: changes from Baseline and percent changes from Baseline: using an analysis of (co)variance model with factors treatment, baseline value, region and previous use of biologics.
- Time to response (ACR20/50/70) will be analyzed using Kaplan-Meier survival techniques, and groups will be compared against placebo using a Cox proportional hazards regression model with factors treatment, region and previous use of biologics.

Other applicable factors, if any, will also be included in the models. Quality of life data (FACIT fatigue scale and SF-36 questionnaire) will be analyzed descriptively. Exploratory between-group comparisons will also be done at each post-Baseline time point using analysis of (co)variance models on the changes from Baseline with factors treatment, Baseline value, region and previous use of biologics.

Handling of discontinued subjects during the 24-week treatment period:

- Subjects who discontinue within the first week so that ACR20/50/70 responses cannot be determined will be classified as nonresponders.

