6.1.2.3. Methods of analysis

Efficacy data (ACR20, ACR50, ACR70, ACR-N, DAS28(CRP), EULAR response, and ACR/EULAR remission, and components of the ACR, CDAI and SDAI at each post dosing visit) will be analyzed descriptively.

The efficacy analysis will present the results in 2 chapters:

1. Chapter 2: Analysis of the full 24 weeks study period.
2. Chapter 3: Analysis of the second study period, from Week 12 onwards.

All chapters will use the original baseline visit as reference.

Handling of discontinued subjects during the 24 weeks treatment period:

- Subjects who discontinue within the first week so that ACR20/50/70 responses cannot be determined will be classified as non-responders.
- For all discontinued subjects, visits after their discontinuation will be imputed for a duration depending on the analysis chapter:
 - Chapter 2: subjects discontinuing during the first study period will have their remaining visits imputed up to and including Week 12.
 - Chapter 2: subjects discontinuing the study will be imputed up to and including Week 24, irrespective of whether they discontinued during the first or second study period.
 - Chapter 3: subjects discontinuing during the first study period will not be imputed during the second study period. Subjects discontinuing during the second study period will be imputed up to and including Week 24.

The method of imputation will depend on the parameter: NRI and LOCF for binary data; LOCF for ordinal or continuous data. Observed-case will always be presented as well.

All non-responding subjects from the lowest dose group who are re-randomized at Week 12 will be handled as follows, again depending on the analysis chapter:

- Chapter 2: their original treatment group of the first study period will be used. The Week 12 value will be carried forward to all further time points (and between-group comparisons) after Week 12.
- Chapter 3: their actual assessments on Weeks 16-20-24 will be analyzed descriptively using the new treatment groups.
- See also: overview table, section 2.1.

All placebo subjects switch to 100 mg q.d. at Week 12. As a result, no placebo group will be available during the second part of the study (chapters 2 and 3).

Between-group comparisons will be done for each dose group versus the placebo group (up to Week 12; not after Week 12). Hommel's closed-testing correction procedure (as implemented in SAS PROC MULTTEST) will be applied to adjust for multiplicity.

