8. DEFINITIONS OF EFFICACY TABLES, LISTINGS AND FIGURES

Mock tables, listings and figures are provided in a separate document.

All analyses will be run on the ITT population, unless specified otherwise.

General comment on the efficacy data listings: listings will present the observed-case time points, with imputed data (for components) clearly flagged. The LOCF- or NRI-imputed time points will not be shown.

General comments on the observed-case analysis:

- Is done for efficacy tables and listings, but not for efficacy plots.
- Is done for all time points in the descriptive statistics.
- Is done for Week 12 only in the inferential statistics.
- Is done for ITT only; not for per-protocol.

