8.1. ACR20, ACR50, ACR70 AND ACR-N**8.1.1. Parameters**

ACR20 response when:

- $\geq 20\%$ improvement from baseline in SJC66, and
- $\geq 20\%$ improvement from baseline in TJC68, and
- $\geq 20\%$ improvement from baseline in at least 3 of the following 5 items:
 - Pain VAS (taken from the HAQ-DI)
 - Patient's Global Assessment of Disease Activity VAS
 - Physician's Global Assessment of Disease Activity VAS
 - Total HAQ-DI score
 - CRP.

Subjects who do not meet this criterion are non-responders.

If any of the 7 components of the ACR20 would be missing, then this missing component will be imputed using the value of the last preceding nonmissing visit. If all components are missing, then the derived ACR20 will remain missing. Imputation of such cases for the tables will be done there using LOCF or NRI like any other missing value.

Subjects who discontinue within the first week so that ACR20/50/70 responses cannot be determined will be classified as non-responders.

The ACR50 and ACR70 responses are derived using the same algorithm, but with 50% and 70% cutoffs respectively.

Note that the primary endpoint of the study is the ACR20 at Week 12 in the ITT population, using NRI imputation.

The ACR-N is derived using the following formula:

ACR-N = MIN [% improvement in TJC68, % improvement in SJC66, MED % improvement in (patient's global assessment, physician's global assessment, patient's assessment of pain, HAQ-DI, CRP)]

So this is taking the smallest of the percentage increases in SJC66, TJC68, and the third of the remaining 5 parameters. In case the ACR-N is negative (i.e., the subject actually worsens instead of improves), then the ACR-N is replaced by a 0. The ACR-N is therefore a number between 0 and 100.

The ACR-N represents the percentage NN% according to which the subjects would have been an "ACRNN" responder.

(See further sections on how to derive these components.)

The time to ACR20 response

= (date of first time ACR20 response is reached) – (date of first medication intake) + 1 day, if the subject achieved ACR20 response during the initial 12 weeks treatment period, or
= MIN (date of the Week 12 visit, date of trial termination) – (date of first medication intake) + 1 day, in case the subject did not achieve ACR20 response at any time during the initial 12 weeks treatment period.

Next to this, the visit during which the ACR20 response was first recorded will be analyzed as well:

- Week 1
- Week 2
- Week 4
- Week 8
- Week 12

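### The primary ACR20 analysis set leaves out treated subjects with no post-baseline efficacy data, and no sentence says how this fits with the rule scoring undeterminable first-week leavers as non-responders

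*SAP*

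**What the plan says.** SAP 8.1.1 fixes the primary analysis: "Note that the primary endpoint of the study is the ACR20 at Week 12 in the ITT population, using NRI imputation". SAP 2.1.1 admits to ITT "all subjects randomized, exposed at least once, and with post-baseline data for at least one efficacy parameter". Protocol 8.8.1.1 has the same restriction, for randomised subjects who "received at least one dose of study medication and have at least one post-Baseline efficacy assessment", and the Protocol Synopsis agrees: "The efficacy analysis will be performed on all subjects who used the study medication at least once and have post-Baseline efficacy data".

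The Protocol's Methods of Analysis adds a rule for early leavers: "Subjects who discontinue within the first week so that ACR20/50/70 responses cannot be determined will be classified as nonresponders". The SAP repeats it in 6.1.2.3 and 8.1.1. None of the three places names the analysis set in which the rule acts.

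Three SAP provisions bear on the order of the steps. Section 8 sets a default for efficacy: "All analyses will be run on the ITT population, unless specified otherwise". Section 7.3 plans Listing 16.2.3.2, which covers subjects in the Safety population but not in ITT. Section 8.1.1 carries single missing ACR components forward, and otherwise: "If all components are missing, then the derived ACR20 will remain missing", to be filled by NRI or LOCF when the tables are made.

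**The concern.** For one kind of subject the two provisions pull apart. Someone who takes study drug, leaves in the first week and provides no post-baseline efficacy data is outside ITT by definition and a non-responder by the first-week rule. The programmer has to infer which governs.

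The likelier reading, exclusion, also deserves attention in itself. It makes the primary denominator depend on something that happens after randomisation, namely whether any efficacy datum was collected. NRI exists to deal with such subjects: it would score them as failures. Someone who leaves after week 1 without efficacy data is excluded too, and the first-week rule does not reach that subject at all.

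The group need not be empty. Under Protocol 8.3.4 withdrawing subjects are only encouraged to complete final evaluations, and loss to follow-up is a listed reason for stopping. SAP 2.3.2 disqualifies efficacy data from the moment of unblinding.

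**Working it through.** **Planning figures.** Protocol 8.8.2 gives n=70 per arm, alpha 5%/3 per comparison, and the rates used below. The pooled chi-square formula is power = Φ{[|p1−p0|√n − z√(2p̄(1−p̄))] / √(p0(1−p0)+p1(1−p1))}. With two-sided alpha 0.05/3, z = 2.394. For 43% v 15%: (0.28×8.367 − 2.394×0.642)/0.610 = 1.32, so power is 90.7%. The others are 89.1% (70 v 40), 79.8% (39 v 15) and 80.0% (67 v 40). The stated 90% and 80% reproduce and are not in dispute.

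**Assumption.** Let k be the treated subjects per arm without post-baseline efficacy data. The documents give no k; 0 to 3 is assumed. Counts near the planned rates are 10/70 (15%), 28/70 (40%), 30/70 (43%) and 49/70 (70%). For 15%, 11/70 is equally close.

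**Effect on one arm.** Excluded subjects would otherwise be non-responders, so r/70 becomes r/(70−k), a rise of rk/[70(70−k)]. In percentage points:

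| Count | k=1 | k=2 | k=3 |
|---|---|---|---|
| 10/70 | 0.21 | 0.42 | 0.64 |
| 28/70 | 0.58 | 1.18 | 1.79 |
| 30/70 | 0.62 | 1.26 | 1.92 |
| 49/70 | 1.01 | 2.06 | 3.13 |

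The first exclusion adds 0.21 to 1.01 points. Later ones add slightly more; at 49/70 the third adds 1.08.

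**Effect on the difference, k=1 to 3.**

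| Subjects lost from | 43 v 15 | 70 v 40 |
|---|---|---|
| Active only | +0.62 to +1.92 | +1.01 to +3.13 |
| Placebo only | −0.21 to −0.64 | −0.58 to −1.79 |
| Both equally | +0.41 to +1.28 | +0.43 to +1.34 |

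**Effect on the test at the planning effects.** This is a logistic Wald test with treatment only; region and prior biologics are omitted for want of data. The log odds ratio is ln[r1/(n1−r1)] − ln[r0/(n0−r0)], and its variance is the sum of the four reciprocal cell counts. For 30/70 v 10/70: 1.504/√0.175 = 3.60, p = 0.00032.

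| Exclusions | 30 v 10 | 49 v 28 |
|---|---|---|
| none | 0.00032 | 0.00045 |
| 3 active | 0.00017 | 0.00013 |
| 3 placebo | 0.00053 | 0.00105 |
| 3 in each | 0.00028 | 0.00032 |

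Three times the largest value, an upper bound for the Hommel adjustment, is 0.0031. Using 11/70 for placebo doubles the first entry to 0.00064 and leaves the conclusion unchanged.

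**Constructed borderline cases, placebo 28/70.**

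- Doses 34, 38 and 42 of 70: raw p 0.3079, 0.0916 and 0.0188; top-dose Hommel p 0.0563. Excluding one top-dose non-responder (42/69) gives raw 0.0146 and adjusted 0.0438.
- Doses 40, 41 and 42 of 70: adjusted p 0.0435, 0.0435 and 0.0434. The same top-dose exclusion leaves that dose at 0.0434. Excluding one placebo non-responder (28/69) moves all three to 0.0519.

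**Power if these subjects are counted.** Here the planned rates are taken to hold among subjects with data. With k=3 in each arm, excluding v counting gives 87.5% v 85.4% (70 v 40) and 89.2% v 88.5% (43 v 15). For 70 v 40 with k=3 in one arm only, it is 88.3% v 80.0% (active) and 88.3% v 92.6% (placebo).

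**The case against.** The strongest reply is that the order is already settled. ITT is the default for efficacy, the primary analysis is placed in ITT, and a listing of exposed subjects outside ITT is planned. The first-week rule assigns a response and says nothing about membership. The rule also has a role inside ITT: a subject whose only post-baseline data are FACIT or SF-36 enters ITT with every ACR component missing, and the rule supplies a non-response where LOCF has no earlier ACR20 to carry. This stands. A reader might infer a flat contradiction, or a rule with no function unless it overrides ITT; the documents support neither.

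Second, the impact is hypothetical. One parameter suffices for ITT entry. The early discontinuation visit collects every ACR component (Protocol 8.6.2.8 and flow chart) and can fall in the Week 1 window from Day 2 (SAP 3.3). The borderline counts are invented, with a top-dose difference of 20 points (60% v 40%) against the 24 to 30 points the trial was powered for. That stands too, and it keeps the point minor.

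Third, one clarifying sentence would remove the ambiguity without touching the primary set after an unblinded interim. True, but it would leave the denominator dependent on a post-randomisation event that NRI can handle at almost no cost. The timing calls for disclosure and a fallback.

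A reader might also cite the intention-to-treat remark in SAP 2.4.1 against exclusion. That section concerns assigned versus actual treatment and does not govern who enters the denominator.

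**Conclusion.** The point holds as a minor one. The primary ACR20 set excludes treated subjects without post-baseline efficacy data. The intended order, filter first and response second, is implied but not stated, and leavers after week 1 without data are covered by no non-responder rule that reaches them.

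Exclusion raises an arm's rate by up to 3.13 points at k=3. It would be tempting to say that exclusion favours the drug. The documents do not support that: the difference falls when placebo loses the subjects and rises when the active arm does. Nor do they show that the trial's conclusion is at risk, since at the planning effects adjusted p stays at or below 0.0031. A result close to 0.05 could cross in either direction, or not move, depending on which arm loses a subject and on all three doses under Hommel.

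These sizes rest on an assumed k of 0 to 3 per arm, counts near the planned rates, and a treatment-only model. If k is zero, the two readings coincide.

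**What to change.** For the binary ACR20 NRI analysis, use all randomised subjects who took at least one dose (the membership SAP 2.1.2 uses for safety), analysed in the randomised arm. Count those without post-baseline efficacy data as non-responders. SAP 4.2 already keeps imputed values in the denominator. State in SAP 2.1.1 that the first-week rule and NRI apply to these subjects, whenever they left.

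Show the current ITT result beside it, labelled modified ITT. This keeps comparability with the interim ACR20 table, which was specified for ITT only. Record in SAP 6.3.2 that the change was made after the interim: the sponsor views the unblinded summaries (SAP 6.2), and SAP version 2.0 itself follows the interim lock.

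If the sponsor will not change the primary set after the interim, run the all-treated NRI analysis as a sensitivity analysis specified before final database lock, and add one sentence saying that ITT membership is decided first. LOCF endpoints can stay as they are, and the Protocol need not be rewritten.

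The cost is one extra run, disclosure of a post-interim change, and possibly slightly lower reported response rates.
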